### 3.1. Study Design

This large randomized pragmatic clinical trial aims to study event rates for benefits (effectiveness) and harms (safety) endpoints associated with the three most commonly employed VTE prophylaxis regimens representing the current spectrum of clinical orthopaedic practice in North America. Our hypothesis is that prevention of clinically meaningful venous thromboembolism (VTE: PE and DVT) and death after total hip and knee replacement with aspirin *will not be inferior to* low intensity warfarin (INR 2.0) or rivaroxaban, a direct factor Xa inhibitor that significantly reduces venographic thrombosis rates, and will be associated with fewer late consequences of adverse bleeding, such as reoperation, infection, and myocardial infarction, that compromise patient reported outcomes related to long term joint-specific function and general well-being. All patients will utilize in-hospital mechanical compression devices in accordance with local standard practice. The study design and approach of this pragmatic clinical trial balance generalizability and internal validity with a design (randomized, three-group parallel design and analysis) that sets standards for internal validity and approach (few exclusion criteria, large number of geographically diverse clinical sites, simple and commonly used treatments administered as best possible with local resources, treatment administration and follow-up in community settings, patients living in the community under no unusual social constraints, outcomes that are big medical events based on death or hospitalization that are easily recognizable and of importance to patients, and no collection of non-essential data) and enhances generalizability. Inclusion criteria are broad, extending to virtually all patients 21 years of age or older undergoing primary or revision hip or knee replacement. Concomitant patient care is at discretion of individual treating surgeons, and follow-up visits are scheduled according to the surgeon's routine and clinical indication only.

The proposed study period will now encompass approximately 10 years: 9 mos for preliminary work; 97 months of patient enrollment; 6 mos trailing follow-up after closure of enrollment; and 6 mos final data analysis. Each site will enroll approximately 1,000 patients over three years for an average annual site enrollment of 333 patients. Each site will aim to reach this goal of 1,000 patients with recruitment continuing at all sites until the overall study enrollment goal is met. With anticipation of no more than a 10% rate of loss to follow-up, which is a conservatively high number in this elective patient population with planned lifetime follow-up, the study will result in enrollment of 18,829 patients with complete follow-up for primary outcome endpoints in approximately 18,000. Nevertheless, a concerted and proactive effort will be required to capture outcome assessment data consistently at the pre-specified time points. We will recruit patients locally within the geographic region of each participating institution to the practices of all participating surgeons in those institutions. Regional advertisement of the trial will assist in recruitment as will the fact that the trial involves only FDA approved drugs endorsed by current clinical guidelines without use of any “experimental” agents. National patient advocacy organizations involved as stakeholders in the trial will assist in publicizing trial recruitment and results.

#### Covid-19 Sub-Study

For most patients, only one additional contact will be required to accomplish the proposed enhancement but this supplemental investigation will not hinder, alter, or interfere with ongoing operations of PEPPER. This incremental data collection will easily integrate with ongoing PEPPER processes and will complement existing data files and patient preference analyses regarding VTE and risk tolerance relative to anticoagulant choice as well as pursuit of discretionary surgery. Active enrollment in the PEPPER trial is now on “pause” until elective THA and TKA are resumed at the participating sites, which began at some sites as of May 4, 2020. During this hiatus, patients whose scheduled procedures have been postponed can still be accessed for the proposed baseline data collection and follow-up on this study cohort will occur with the restart of elective surgeries.

**Recruitment Plan**

Total number of study participants expected to be screened across approximately 25 sites	112,650
Of those screened, total number of study participants expected to be eligible (90%)	101,385
Target enrollment (18% of screened)	20,000
Target sample size with complete follow-up (accounting for 10% loss to follow-up)	18,000

**3.1.1. Participating Sites**

Approximately twenty-five field sites have been identified and have committed to randomization of patients to the treatment groups. Each site has been selected based upon the expertise of the operating surgeons in total joint replacement, the commitment and culture of the institution to support high quality clinical research, a past history of institutional involvement in clinical data collection with a high degree of reliability and accuracy, and the ability to recruit sufficient patient numbers to meet enrollment targets. Each of the included sites has been successfully involved in clinical trials in the past.

The consortium of approximately 25 study centers accounts for 37,550 THA and TKA per year, resulting in a conservative projected enrollment rate of 18% (20,000/112,650) of all procedures performed. Previous elective surgical trial enrollment rates from these sites has ranged from 33% to 60%, and a pre-application patient survey (Appendix C) suggests that more than 50% of patients undergoing elective THA/TKA would be willing to be randomized. We projected a pre-Covid 22% recruitment yield with confidence because our clinical sites have track records this good or better and, as a pragmatic clinical trial, PEPPER has no placebo groups, all interventions are currently accepted treatments, and PEPPER has avoided both profusion and complexity of eligibility criteria, which are usual reasons for failure to recruit adequately in clinical trials.

**3.1.2. Study Procedures**

*In May 2023, PCORI approved the removal of the warfarin arm of the trial due to increasing institutional barriers, such as the prevalence of home health and the inability to receive INR testing, owing to the pandemic. All patients enrolled after the approval of this protocol and all subsequent site-specific approvals will use a 1:1 rivaroxaban: aspirin randomization scheme. Patients who were enrolled and randomized into the warfarin arm of PEPPER prior to this protocol approval will remain in the trial, continue to receive warfarin, and be followed for data collection as needed per the protocol. The data collected on all warfarin patients will be analyzed as described in the analysis section.*

**a) Screening and Enrollment**

Approximately 20,000 eligible patients undergoing elective primary or revision hip or knee joint replacement will be enrolled at approximately 25 centers. Initial screening will occur of all consecutive patients scheduled for elective total hip or knee replacement in the practices of participating surgeons; while screening criteria will be reviewed by the local study coordinators, physician confirmation will be required before a patient is determined eligible for enrollment into the trial. All consecutive eligible patients will be approached for entry and must agree to randomization to participate in the trial. With a goal of 25 centers enrolling approximately 20,000 patients at a rate of about 1,000 per center over eight years, the rate of enrollment is 267 patients per center per year or 6 patients/week for one study coordinator working 48 weeks/year. Sites may continue to enroll past the 1,000 patient goal until the overall study enrollment goal is met. A signed informed consent form will be obtained before performing any study procedures that go beyond standard clinical care. A subject is considered enrolled when all eligibility criteria have been documented as being met and the institutional consent form (ICF) is signed.

Initial discussion and introduction to the study will occur with the treating surgeon in the course of an outpatient appointment at the time of patient decision to pursue elective THA or TKA, primary or revision. Informational materials about the study can be distributed at this time and the operating surgeon should uniformly endorse participation of all eligible patients in the study. At any point prior to surgery, should the prospective study patient have any questions regarding the procedures of the study, a study staff member and/or the surgeon will answer all questions to the patient's satisfaction.

Participants may be consented using two methods:

1. **In-person Recruitment:** The PEPPER site coordinator and/or surgeon meets with potential participants in person to review the trial and obtain informed consent and signed documents through paper consent forms or e-consenting via REDCap. A copy of the signed consent form will either be given in person, mailed, or emailed to the participant based on their preference. If the patient remains uncertain about participation, the site coordinator and/or surgeon will contact the patient by phone or video conference to further develop understanding and confidence of the patient to participate in the trial;
2. **Remote Recruitment:** Remote recruitment will occur either when a potential patient has requested more time to review the study or when the patient is not seen during an in-person surgical clearance visit. The potential participant must have the appropriate capabilities to access REDCap (i.e computer, smartphone, or tablet, and an internet connection) and must be in a private location during the consenting process. The coordinator or designated study staff will contact the patient either via phone or video conferencing. The informed consent process will be completed with signatures of all parties obtained via e-consent using REDCap. The signed consent form will then be either emailed or mailed to the participant based on their preference. Remote consenting can occur up to one day prior to surgery.

If a patient is unable to sign the consent form during a pre-operative clinic visit and does not have the necessary capabilities to utilize e-consenting, written consent may be obtained via telephone. Obtaining written consent over the phone may only be done only if the patient has a paper copy of the consent form. The patient will sign their copy of the consent form while the coordinator signs one as well. The patient will either mail, email, or fax their copy to the coordinator who will merge the two copies to form one fully executed consent form. Once the form has been received by the coordinator, the patient can complete the baseline assessments. Baseline assessments must not be completed until the signed copy of the consent form has been received from the patient and co-signed by the coordinator. For those sites that are required to have a separate consent and HIPAA authorization, the HIPAA authorization must also be signed, dated, and sent in via mail or fax in order to begin study procedures.

Consent to participate in the study may be obtained by the study site coordinator or any other appropriately qualified study staff member. Upon obtaining informed consent, each site coordinator will collect baseline information from the patient concerning comorbidities, joint function, and general well-being data using the respective hip or knee disability and osteoarthritis outcome scores (HOOS and KOOS), the Oswestry and Charlson instruments, and the PROMIS-10 global health survey. Baseline instruments should be collected within the 3 months prior to the patient's operation.

Once consent is obtained, the surgeon will sign off on all eligibility criteria using the Surgeon Screening Confirmation Form and the patient will be considered enrolled in the PEPPER trial and eligible for randomization.

#### **b) Inclusion Criteria**

The Inclusion Criteria for entry into the trial are as follows:

- 1) Males and females 21 years of age or older;
- 2) Undergoing elective primary, resurfacing arthroplasty, revision, or second stage re-implantation total hip replacement;
- 3) Undergoing elective primary, revision, or second stage re-implantation total or uni-compartmental knee replacement;
- 4) Patient is eligible for randomization to at least two of the study anticoagulation regimens;
- 5) Patient has necessary mental capacity to participate and is able to comply with study protocol requirements;
- 6) Patient is willing and able to give informed consent; and
- 7) Patient is willing to be randomized and participate.

#### **c) Exclusion Criteria**

The Exclusion Criteria for entry into the trial are as follows:

- 1) Patients undergoing bilateral hip or knee replacement;

- 2) Patients undergoing total hip or knee replacement who have been enrolled in this study for a prior hip or knee replacement;
- 3) Patients who are concurrently enrolled in another active interventional clinical trial testing a drug or intervention known or believed to interact with aspirin or rivaroxaban;
- 4) Women who are pregnant or breastfeeding, as well as those of reproductive potential unless there is a negative urine pregnancy test on the day of surgery;
- 5) Patients on chronic (longer than the prior 6 months) anticoagulation other than with antiplatelet medications;
- 6) Patients with documented gastrointestinal, cerebral, or other hemorrhage within 3 months of the operation;
- 7) Patients with a known diagnosis of defective hemostasis and past history of clinical bleeding requiring transfusion and treatment;
- 8) Patients who have had an operative procedure involving the eye, ear, or central nervous system within one month;
- 9) Patients with severe uncontrolled hypertension with systolic BP > 220mmHg or diastolic BP > 120mmHg;
- 10) Patients with an absolute body weight of less than 41 kilograms (90.4 lbs) at baseline visit;
- 11) Vulnerable patient populations including prisoners and institutionalized individuals.

If women of child-bearing potential do not already have a urine pregnancy test on the morning of surgery as part of their clinical care, one will be done prior to receiving any study medication. Women of child bearing potential include women who are premenopausal who have not had a bilateral oophorectomy, hysterectomy or tubal ligation. A woman is considered post-menopausal when she has not had a menstrual period for at least one calendar year. Women who have a positive urine pregnancy test on the morning of surgery will be considered a screen fail and will not be eligible to participate in the trial.

#### d) Randomization

Randomization of consented patients occurs after the surgeon confirms eligibility and up until the day before the originally scheduled surgery date. If a patient's surgery is postponed, or cancelled and ultimately rescheduled, the patient will keep the original randomization assignment. The ability to randomize a patient will be available via the web-based randomization system once consent has been signed and all baseline instruments have been entered into the database. Study group assignments will be shared with the surgeon at the time of randomization, and with the patient on the day of operation unless necessary to provide third party insurance coverage for prescribed medical care.

Patients will be assigned to treatment groups using a web-based randomization system. A permuted block randomization scheme will be utilized to ensure equal assignment of patients to each drug study group at each participating site, taking into consideration the noted criteria for stratified randomization. In the absence of any randomization stratification requirements, patients meeting all eligibility criteria without any randomization exclusions will be assigned to one of two groups; a concealed centralized randomization schedule will provide assignment to one of two prophylaxis regimens (aspirin or rivaroxaban) in randomly varying block sizes developed separately for each clinical site and stratified according to type of surgery (hip or knee replacement). Prophylaxis will continue for 30 days, in accordance with clinical guidelines, and pneumatic compression devices will be utilized in hospital in conjunction with both of the treatment groups according to local practice. The two groups are as follows:

- 1) Enteric coated aspirin (regimen with lowest bleeding risk; clinical PE and all-cause mortality rates comparable to more intensive anticoagulants); and
- 2) Rivaroxaban, an oral direct Factor Xa inhibitor (regimen with lowest PE and DVT rate but higher bleeding risk [3-5%]).

A contraindication to one of the two study prophylaxis regimens for venous thromboembolism is exclusionary. The contraindications to aspirin are:

- 1) Patients with a known aspirin allergy;
- 2) Patients with a personal history of PE or DVT;

- 3) Patients with a known condition of thrombophilia proven by diagnostic testing; e.g. Factor V Leiden;
- 4) Patients with a cancer diagnosis who are under active treatment.

The contraindications to rivaroxaban are:

- 1) Patients with a serum creatinine greater than 2.0 mg/dl;
- 2) Patients taking medications that interfere with metabolism of rivaroxaban via CYP 3A4 inhibition.

If, after randomization, a participant is unable to take the specified medication due to financial constraints, or new information becomes available that affects the safety of the participant, the surgeon will use his/her discretion in assigning the patient to the other arm of the trial.

Participants should be withdrawn from the study if they do not receive one of the study medications at the same dosage level being studied in the trial. If a patient received a medication other than a PEPPER approved treatment group and remains on this medication, the patient should be withdrawn from the study regardless of their willingness to be followed.

Please refer to the Manual of Procedures for additional guidelines involving randomization assignments.

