## 3.1.3. Data Analysis

Primary Data Analysis

The unblinded nature of the clinical trial could threaten unbiased comparisons. Randomized patients will not be notified of treatment group assignment until the day of the proposed operation, unless necessary to provide third party insurance coverage for prescribed medical care. Further, our trial is protected from this threat to adherence with treatment assignment by the short course of treatment, the follow-up contact to ascertain treatment, and the motivation of each patient to take prescribed drugs to prevent PE and DVT. The trial is protected from the threat to unbiased outcome ascertainment and classification by the independent centralized contact with patients to determine need for collection of clinical documents, preparation of documents related to readmission or treatment for bleeding or thrombosis to remove any indication of treatment assignment, and blinded outcome classification based upon expert review of the redacted documents by the OAC.

**1.0 Primary Aim 1.** *To compare the frequency of the aggregate clinical endpoint of important venous thromboembolism (clinical PE and DVT leading to hospital readmission) and all-cause mortality.*

**1.1 Risk Estimates.** First, 6-month probabilities of our primary composite endpoint (clinical PE, clinical DVT, and all-cause mortality) by treatment group will be estimated and compared. To address the fact that some participants will have incomplete follow-up (e.g., we may know whether they had an event within 3 months but not for the full 6 months), we will estimate 6-month risk of an event using a Kaplan-Meier approach. Confidence intervals will be based on Greenwood's formula (applied using the delta method to a complementary log-log transformation of the estimated risk). In these calculations, those whose follow-up is incomplete will be censored at the time that the follow-up ends.

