**Table 1. Numbers of patients and resulting power and precision in comparing aspirin to warfarin.**

	Aspirin	Warfarin
Number Randomized as of May 1, 2023	5132	5389
Number Eligible for both treatments (either medically or due to logistics)	4703	4698
Projected number who took the assigned treatment 	4402	3688
Projected number who will have complete follow-up 	3962	3319
Projected width of the 95% CI for the difference in risk of primary outcome	0.96 percentage pts	
Power to obtain evidence of non-inferiority based on 0.69% margin of inferiority	80.3%	
Margin of inferiority detectable with 80% power	0.69 percentage pts	

Based on a crossover rate of 21.5% and 6.4% for Warfarin and Aspirin, respectively.

Assuming that 90% of those randomized have surgery, do not withdraw, and have 6-month follow-up information.

**Recruitment and randomization.** To achieve the total of approximately 18,000 evaluable patients we will recruit approximately 20,000 to accommodate the possibility of 10% loss to follow-up. We will randomize patients with equal probabilities to each of the three regimens using a web-based program provided by Statix. Those sites that are on the restricted randomization plan due to structural barriers will randomize patients using a 1:1 randomization scheme. Following removal of warfarin from the protocol in June 2023, all sites will randomize patients using a 1:1 scheme to either aspirin or rivaroxaban. The web application is available 24/7, password protected, and maintains an audit trail of transactions with time stamp login for users. There will be a separate randomization schedule for each clinical site, stratified according to operation (hip or knee) to ensure balanced intervention groups with respect to site and operation. Within each stratum, assignments will be randomly permuted within repeating blocks of varying size.

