A concealed centralized randomization schedule will provide assignment to one of the prophylaxis regimens, as specified in section 3.1.2b, in randomly varying block sizes of 3, 6, and 9 developed separately for each clinical site and stratified according to type of surgery (hip or knee replacement).

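### Open assignment to the surgeon who confirms eligibility, with permuted blocks inside each site and operation, lets anyone who sees most of a site's list guess the next assignment above chance.

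*Protocol*

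**What the plan says.** Section 3.1.3 of the Protocol concedes that "The unblinded nature of the clinical trial could threaten unbiased comparisons". On who knows what and when, section 3.1.2 d) states "Study group assignments will be shared with the surgeon at the time of randomization". Section 3.1.2 a) adds that, after consent, "the surgeon will sign off on all eligibility criteria using the Surgeon Screening Confirmation Form". The order of the two steps is fixed by 3.1.2 d): "Randomization of consented patients occurs after the surgeon confirms eligibility and up until the day before the originally scheduled surgery date".

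On the lists, the recruitment and randomisation paragraph after Table 1 gives each site its own schedule, stratified by hip or knee, and says "Within each stratum, assignments will be randomly permuted within repeating blocks of varying size". Section 3.1.2 d) likewise speaks only of randomly varying sizes. Section 4.1.1 alone prints the sizes: "in randomly varying block sizes of 3, 6, and 9 developed separately for each clinical site". That section still describes three regimens, whereas 3.1.2 d) now allocates 1:1 between aspirin and rivaroxaban.

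The stated safeguards before allocation are a concealed central web schedule, block sizes that vary at random, and an approach to all consecutive eligible patients.

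**The concern.** A concealed central list hides future assignments, but it does not stop inference from past assignments that are already known. Each permuted block must close in balance, so whoever has followed a stratum knows which drug is behind and therefore more likely to come next. The surgeon then decides on sign-off for the next consented patient, and the randomisation date may fall anywhere between sign-off and the day before surgery.

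The motive is at least plausible. Section 2.2 reports surgeons moving to aspirin and uncertainty in some centres about randomising. If sign-off or timing depended on the expected drug, the arms would differ in baseline risk. The primary comparison is a non-inferiority test with a margin of 0.69 percentage points and a planning event rate of 1.1%, so a small shift counts. The planned weighting (section 1.5.4 of the analysis plan within 3.1.3) lists age, sex, site, date of surgery and education as candidates. None of these is a direct measure of thrombosis or bleeding risk factors such as comorbidity.

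**Working it through.** The Protocol gives no predictability figure, so there is nothing to reproduce.

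**Inputs.**
- Three-arm sizes 3, 6, 9 (section 4.1.1).
- Two-arm sizes: not stated, so assumed and varied.
- Each size equally likely: assumed.
- Share of the list that a surgeon sees: not stated, so varied from all to one sixth.

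**Two arms, whole list visible, by hand.** The guesser names the arm used less so far and tosses a coin when the arms are level. In a block of size 2n the expected number of correct guesses is

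E(n) = n + 2^(2n-1)/C(2n,n) - 1/2.

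This gives E(1) = 1.50, E(2) = 2.83, E(3) = 4.10, E(4) = 5.33, E(5) = 6.53, E(6) = 7.72, E(7) = 8.89, E(8) = 10.05 and E(9) = 11.20. Every block ends level, so the rule needs neither the sizes nor the boundaries. For mixed sizes the accuracy is the sum of E divided by the sum of sizes:

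- {2,4,6}: (1.50 + 2.83 + 4.10)/12 = 70%
- {4,6,8}: (2.83 + 4.10 + 5.33)/18 = 68%
- {6,12,18}: (4.10 + 7.72 + 11.20)/36 = 64%
- {8,10,12,14,16}: (5.33 + 6.53 + 7.72 + 8.89 + 10.05)/60 = 64%

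**Simulation.** A guesser who knows the set of sizes but not the boundaries, and updates by Bayes' rule, gave:

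| Scheme | Correct | Chance | Certain | At least 75% confident |
|---|---|---|---|---|
| Three arms {3,6,9} | 55% | 33% | 4% | 15% |
| Two arms {2,4,6} | 70% | 50% | 4% | 59% |
| Two arms {4,6,8} | 68% | 50% | 2% | 34% |
| Two arms {6,12,18} | 64% | 50% | 2% | 24% |
| Two arms {8,...,16} | 64% | 50% | 0.4% | 14% |

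The least-used-arm rule scored the same overall accuracy as the Bayes guesser in every row. Knowing the sizes therefore does not raise overall accuracy. It mainly identifies the assignments that are certain.

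**Partial sight (Bayes guesser, sizes as assumed).**

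| Share of list seen | Three arms {3,6,9} | Two arms |
|---|---|---|
| 1/2 | 43% | 55-59% |
| 1/3 | 39% | 54-56% |
| 1/4 | 37% | 54-55% |
| 1/6 | 36% | 52-54% |

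**What this could do to the comparison.** Suppose a share s of enrolment is steered, the guess is right with probability c, and the steered patient types differ in risk by D. Then the bias in the risk difference is s x (2c - 1) x D. With D = 1 percentage point (assumed):

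- c = 0.68, s = 10%: 0.10 x 0.36 x 1 = 0.04 points, 5% of the 0.69-point margin
- c = 0.68, s = 25%: 0.25 x 0.36 x 1 = 0.09 points, 13%
- c = 0.56, s = 25%: 0.25 x 0.12 x 1 = 0.03 points, 4%

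Both s and D are illustrative. The documents give neither.

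**The case against.** The strongest reply is about sight of the list. The Protocol says the surgeon is told the assignment. It does not say that surgeons see their colleagues' assignments, and section 3.1 refers to all participating surgeons at each institution. At a third of the list or less, the gain over chance is only about 2-6 points. This stands and limits the claim for individual surgeons. It does not remove it: a sole surgeon sees the whole stratum. Section 3.1.2 a) plans the workload around one coordinator per centre, who handles screening, consent and baseline data. That a coordinator sees most assignments is an inference, though a natural one.

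A reader might infer that the current block sizes are known to sites. The documents do not support this. Sizes 3 and 9 cannot split equally between two arms, so the printed set belongs to the three-arm scheme, and no set is printed for 1:1.

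A reader might also infer that any steering would be undetectable. That is too strong. Baseline instruments, including the Charlson index, must be entered before randomisation, and the web system keeps a time-stamped audit trail. A consented patient refused without a listed reason can be identified. Selection on unmeasured features could still escape.

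Finally, central concealed blocks of varying size are a standard design, the sites have committed to randomisation, and the Manual of Procedures, not at hand, may hold further rules. All true, but nothing in the Protocol itself limits inference from past open assignments.

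**Conclusion.** The point holds in a limited form. With open assignment, surgeon sign-off before randomisation and blocking within site and operation, a person who sees all or most of a list guesses correctly about 55% of the time against 33% (three arms, printed sizes) and about 64-70% against 50% (two arms, assumed sizes). A surgeon who sees a third or less reaches about 52-56% in the two-arm scheme. The cause is openness plus blocking in site-level strata. The printed sizes add mainly the certain cases, about 4% for 3/6/9.

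Separately, section 4.1.1 cannot be right for the present scheme and must be reconciled with section 3.1.2 d) and the paragraph after Table 1.

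The two-arm figures rest on assumed sizes and equal size probabilities. The practical risk rests on how much of the list site staff see, which is not stated. A reader might take this as a finding that allocation was steered. The documents show an opportunity, not an occurrence. The change is worth making because it is cheap, not because the trial is shown to be biased.

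**What to change.** 1. Delete the block sizes from section 4.1.1 and hold them only in the randomisation agent's restricted specification. Bring that section into line with the 1:1 scheme.
2. For remaining two-arm enrolment, have that specification use larger, varied even blocks, for example 8 to 16 in steps of 2. Against assumed current sizes of {4,6,8} or {2,4,6}, this cuts assignments predictable with at least 75% confidence from about 34-59% to about 14%. Overall accuracy falls only from about 68-70% to 64%, so the gain lies mainly in the confident guesses.
3. Use the audit trail and baseline data to reconstruct the predicted assignment for each patient, and test whether baseline risk is related to it. This also covers patients already randomised, whom items 1 and 2 cannot reach.

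Cost: a wording deletion, a change in the existing web system, and one extra analysis. The downside is slightly larger possible imbalance within a stratum. The greatest gap between arms is half the block, so 8 patients with blocks of 16 against 3 with blocks of 6. Planned strata over the whole trial average about 267 hip and 533 knee patients per site (20,000/25 = 800, split one third to two thirds), but what remains to be enrolled in each is smaller.

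I would not ask the system to impose an order by surgery date. Remote consent is allowed up to the day before surgery and operations are rescheduled, so that is not a simple configuration change.
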